This is a pilot trial to determine the dose efficacy and safety of droxidopa to increase systemic BP and improve orthostatic BP and CBFv responses compared to placebo in hypotensive individuals with SCI. Because this is a pilot trial, the following statistical analyses are not powered for a specific effect size; however, the results will be used to power a subsequent large scale clinical trial to identify the utility and safety of droxidopa for treatment of asymptomatic hypotension in persons with SCI.

Primary Aim 1.1: Dose optimization, open-label trial to determine the proportion of subjects with SCI with a normotensive response to droxidopa (**Efficacy #1**). Normotension will be defined as an average systolic BP (SBP) recorded 60-120 minutes after dose administration of between 111-139 mmHg in males and 101-139 mmHg in females.

- **Hypothesis 1.1** – Seated SBP will be normalized in 60% of the study sample following administration of droxidopa.
 - This hypothesis will be tested by constructing a 95% confidence interval about the sample proportion of cases in which BP is normalized with droxidopa. The inclusion of the 60% value in the confidence interval will be taken as evidence in support of the hypothesis. Further, the point estimate and confidence interval will provide the first reported estimate of the BP normalizing effect of droxidopa in the population with SCI.

Primary Aim 1.2: Dose optimization, open-label trial to determine the proportion of subjects with SCI with a hypertensive response to droxidopa (**Safety #1**). Hypertension will be defined as a sustained elevation in seated SBP \geq 140/100 mmHg or intolerable side effects considered related to study medication

- **Hypothesis 1.2** – Less than 10% of the study sample will exhibit hypertension or intolerable side effects related to administration of droxidopa.

- This hypothesis will be tested by constructing a 95% confidence interval about the proportion of cases in which either seated BP $\geq 140/100$ or intolerable side effects occur. If the 95% CI excludes values $\geq 10\%$, this will be taken as evidence in support of the hypothesis. Further, the point estimate and confidence interval will provide the first reported estimate of the expected side effects of droxidopa treatment in the population with SCI.

Secondary Aims: To determine the effect of the individualized optimal dose of droxidopa, compared to placebo, on (1) supine BP (**Safety #2**), (2) SBP during a head-up tilt (HUT) maneuver to 70° (**Efficacy #2**) and change in cerebral blood flow velocity (CBFv) from supine to HUT (**Efficacy #3**). The following hypotheses will be tested in hypotensive individuals with SCI:

- **Hypothesis 2.1A** – Average supine SBP will be significantly increased following droxidopa administration compared to placebo.
 - This hypothesis will be tested using a repeated measures analysis of covariance where the pre-droxidopa or placebo SBP will be used as the covariate and the adjusted post-test scores will serve as the dependent variable. In addition, the covariate adjusted point estimate and 95% confidence interval of the difference between drug conditions will provide the first reported estimate of the supine SBP response to droxidopa versus placebo in the SCI population.
- **Hypothesis 2.1B** – The proportion of supine BP observations $\geq 140/100$ mmHg following droxidopa administration will not differ significantly from the proportion observed during the placebo trial.
 - This hypothesis will be tested by performing separate (one each for systolic and diastolic pressure) tests of the differences between dependent proportions, from which the 95% confidence intervals will be calculated. The presence of zero in a confidence interval will indicate a lack of statistical difference in incidence of hypertensive events between the droxidopa and placebo conditions.
- **Hypothesis 2.2** – Average SBP during 70° HUT will be significantly increased following droxidopa administration compared to placebo.
 - This hypothesis will be tested by performing a dependent t-test between the mean SBP during 70° HUT comparing droxidopa to placebo. Further, the point estimate and resulting 95% confidence interval will provide an estimate of the SBP response to HUT of droxidopa versus placebo in the SCI population.
- **Hypothesis 2.3** – The change in CBFv from supine to HUT will be significantly attenuated following droxidopa administration compared to placebo.
 - This hypothesis will be tested using a repeated measures analysis of covariance where the pre-HUT CBFv will be used as the covariate and the adjusted post-HUT CBFv scores will serve as the dependent variable. In addition, the covariate adjusted point estimate and 95% confidence interval of the differences between drug conditions (droxidopa vs. placebo) will provide the first reported estimate describing the effect of droxidopa on the CBFv response to HUT.
- **Hypothesis 2.4** – Plasma renin and serum aldosterone concentrations will be reduced and plasma norepinephrine concentrations will be increased during HUT following administration of droxidopa compared to placebo.
 - These hypotheses will be tested using a repeated measures analysis of covariance where the pre-HUT concentrations will be used as the covariate and the adjusted post-HUT concentrations will serve as the dependent variable. In addition, the covariate adjusted point estimate and 95% confidence interval of the differences between drug conditions (droxidopa vs. placebo) will provide the first

reported estimate describing the effect of droxidopa on these vasoactive substances in response to HUT.

Safety Monitoring:

As is stated in the consent forms there is a risk of increased systemic blood pressure following administration of droxidopa.

Laboratory Monitoring: During the laboratory observation heart rate and blood pressure will be closely monitored at 15 minute intervals and action will be taken if blood pressure is elevated above 140/90 mmHg for more than 30 minutes. The action plan to lower blood pressure in the laboratory is as follows:

1. Loosening of clothing or braces
2. Re-positioning the participant in his/her wheelchair
3. Emptying of the bladder/catheter bag

If these measures prove unsuccessful in lowering blood pressure the study physician will be alerted and brought to the laboratory for further subject monitoring and administration of an anti-hypertensive agent if deemed necessary. The medication of choice will be sub-lingual nitroglycerin.

The study clinician, [name] will monitor and review all blood pressure recordings during each laboratory visit in both Study 1 and 2. Although he will not be in the laboratory for the duration of testing, his office is across the hall and he is readily accessible if needed.

Testing will be scheduled when [name] is in the office only.

Because Study 2 is a randomized blinded placebo controlled trial we have included a data safety monitor to review individual blood pressure responses and trends in hemodynamic and symptoms in aggregate data. [name], MD will be an independent clinical monitor, he will have a copy of the randomization code and will contact study investigators if a concern arises pertaining to a study participant and will be in contact with the participant who may be experiencing increased symptoms related to AD.

Home Monitoring: Participants will be monitored for 4 hours or until their blood pressure has returned to baseline levels ($\pm 10/5$ mmHg). No subject will be sent home with a blood pressure that is elevated above 140/90 mmHg. However, if blood pressure remains above their baseline, **but not in the hypertensive range**, after 4-hours of testing they may be sent home with a 24-hour blood pressure monitor, which will be programmed to obtain a blood pressure reading every 20 minutes during the day and at 30-minute intervals during the night. The study coordinator or the PI will follow-up by phone with the subject to asses any adverse side effects and to document blood pressure changes. The subject will be asked to immediately report any significant AE they may feel after leaving the laboratory.

Literature Cited

1. Claydon, V.E. and A.V. Krassioukov, *Orthostatic hypotension and autonomic pathways after spinal cord injury*. J Neurotrauma, 2006. **23**(12): p. 1713-25.
2. Guttmann, L., et al., *Effect of Tilting on the Cardiovascular Responses and Plasma Catecholamine Levels in Spinal Man*. Paraplegia, 1963. **1**: p. 4-18.
3. Mathias, C.J., et al., *Plasma catecholamines, plasma renin activity and plasma aldosterone in tetraplegic man, horizontal and tilted*. Clin Sci Mol Med, 1975. **49**(4): p. 291-9.
4. Wecht, J.M., et al., *Direct and reflexive effects of nitric oxide synthase inhibition on blood pressure*. Am J Physiol Heart Circ Physiol, 2008. **294**(1): p. H190-7.
5. Wecht, J.M., et al., *A prospective report on the prevalence of heart rate and blood pressure abnormalities in veterans with spinal cord injuries*. J Spinal Cord Med, 2013. **36**(5): p. 454-62.
6. Zhu, C., et al., *A retrospective chart review of heart rate and blood pressure abnormalities in veterans with spinal cord injury*. J Spinal Cord Med, 2013. **36**(5): p. 463-75.

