traumatic SCI [23] and 3) an open-label dose escalation trial in 10 individuals with chronic SCI (C3-T10). [16] In the first case report droxidopa (600 mg) was associated with a 10-fold increase in plasma NE, an attenuated fall in orthostatic BP and marked reduction in symptoms of orthostatic intolerance. [26] In the second case report droxidopa (300 mg BID) was associated with an attenuated fall in seated BP and improved symptoms of orthostatic intolerance. [23] It should be noted that BP was not normalized in these two case reports, but subjects reported less symptomatic OH. Results from the dose escalation trial suggest that a single dose of droxidopa (400 mg) normalized seated SBP in 5 of the 10 subjects tested, with limited evidence of supine or seated hypertension; however, the BP response to droxidopa waned over time and by 4-hours post-drug BP was not significantly different from pre-drug levels. [16] These reports highlight the need for a more thorough investigation of dose effectiveness for achieving adequate orthostatic BP control, prior to wide spread use in the SCI population.

[figure not shown]
[figure not shown]
[figure not shown]
Preliminary Data:

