double-blind, placebo-controlled trial. Preliminary data on the mean seated SBP response to midodrine compared to placebo is presented in 21 hypotensive subjects with SCI (Figure 1). The results suggest significantly elevated SBP following midodrine (10 mg) administration compared to the other 3 conditions; however, individuals responses to midodrine varied significantly (Figure 2). In fact only one-third of the subjects tested (7 subjects) responded to midodrine with a normal SBP (between red dashed lines); 7 remained hypotensive and 7 had hypertensive responses. Furthermore, compared to placebo (Figure 3A), the percentage of SBP recordings reflecting systolic hypertension (i.e., ≥ 140 mmHg) following midodrine administration (Figure 3B) was significantly increased ($p<0.01$) over the 4-hour observation, whereas the percent of normotensive SBP observations was unchanged. Collectively these data suggest that midodrine is effective at normalizing SBP in some hypotensive individuals with SCI, but resulted in seated systolic hypertension in one-third of the population tested.

Droxidopa is a prodrug that is converted to NE, which binds to alpha-receptors and causes increases in orthostatic BP. We have demonstrated that 400 mg oral administration of droxidopa significantly increases seated SBP in hypotensive individuals with SCI; however, individual responses varied. [16] The proportion of SBP recordings within the normotensive range (i.e., 111-139 mmHg) did not differ from the no-drug trial (**Figure 4A**) following administration of either the 100 mg (**Figure 4B**) or 200 mg (**Figure 4C**) dose of droxidopa; however, the 400 mg dose (**Figure 4D**) did appear to increase the proportion of normal SBP recordings ($42.3 \pm 28.5\%$) over a 3-hour seated observation compared to the no-drug ($19.3 \pm 29.5\%$), 100 mg ($11.8 \pm 23.3\%$) and 200 mg ($18.9 \pm 21.8\%$) trials, although this difference was not statistically significant. Three individuals each had a single recording of a seated SBP ≥ 140 mmHg (156, 150, 149 mmHg), which was observed during the first 30-minutes, and constituted 3% of all observed SBP recordings (**Figure 4D**). Individual seated SBP responses (mmHg) to droxidopa, averaged over the 3-hour observation, is presented (**Figure 5**). As depicted (**Figure 5A**), 5 individuals responded to the 400 mg dose with a SBP \geq

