significantly increased in those who responded to the 400 mg dose of droxidopa compared to the non-responders (105 ± 10 vs. 81 ± 10 mmHg, respectively; $p=0.0048$), and although the magnitude of effect was doubled in the non-responders, the SBP response did not differ significantly (9.0 ± 10 vs. 18.6 ± 16 mmHg, respectively; $p=0.2937$). These data suggest that individuals with a seated SBP below 95 mmHg may need a higher dose of droxidopa to normalize SBP.

d) Research Design and Methods

We propose to determine the dose of droxidopa that normalizes seated SBP in hypotensive individuals with SCI, and to determine the effect of that dose of droxidopa on supine BP, orthostatic BP and CBFv compared to placebo.

Study Population: Fifty subjects with SCI will be screened for study eligibility. We anticipate that approximately 40 of the subjects screened will be eligible and will undergo the dose optimization trial (**Study 1**). We anticipate that 25 subjects will respond to droxidopa with a normal seated SBP, and these individuals will be eligible for the randomized placebo-controlled trial to determine the effect of the optimal dose on supine BP, orthostatic BP and CBFv compared to placebo (**Study 2**). Each subject will be randomized by the Research Pharmacy to receive either droxidopa/placebo or placebo/droxidopa for the placebo-controlled prospective trial. Randomization will occur in a double-blinded manner. Study medication and placebo will be distributed by the James J Peters VAMC Pharmacy Service. The study is proposed to be completed in two years. Total enrollment will be accomplished within 18 months of obtaining full IRB approval, which should be complete within 6 months of funding, and subject participation is estimated to last about 6-8 weeks. A complete description of the study population can be found in the Human Subjects Form 11.

Study Procedures: Identical testing procedures will be performed at the JJP VAMC and the ISMMS according to the table below.

Procedures Table	Screening	Study 1									Study 2	
		1	2	3	4	5	6	7	8	9	10	11
Visit												
Medical Intake	X											
Medical History	X											
OH Survey	X											
AD Survey	X											
Seated BP	X	X	X	X	X	X	X	X	X	X	X	
Supine BP	X										X	X
HUT BP											X	X
CBFv											X	X
Side-effects		X	X	X	X	X	X	X	X	X	X	X
OH Symptoms Survey											X	X
Fatigue Survey	X										X	X

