Study 1– To determine the proportion of subjects with SCI with: 1.1) a normotensive response to droxidopa and 1.2) a sustained hypertensive response to droxidopa. The dose optimization study will be scheduled to begin after completion of the screening visit. Eligible participants will be administered oral droxidopa in a dose escalation, open-label manner beginning with 200 mg. The dose will be adjusted upwards by 100 mg on subsequent visits until (1) average SBP recorded 60-120 minutes after dose administration is 111-139 mmHg in males and 101-139 mmHg in females (i.e., normotensive), (2) sustained elevation (\geq 30 consecutive minutes) in seated SBP \geq 140/100 mmHg, (3) maximum dose of 800 mg is reached without adequate SBP response or (4) intolerable side effects considered related to study medication. Subjects will visit the testing laboratory on as few as 1 (200 mg) and as many as 8 (800 mg) days, and will be asked to refrain from taking prescription anti-hypotensive agents for 12 hours prior to study. Participants with an excessive response to the 200mg dose, i.e., average 4-hour SBP above 139, will be asked to visit the laboratory to determine their blood pressure response to a 100mg dose. Based on our previous data, we do not anticipate an excessive response to the 200mg dose in most participants, we request the addition of the 100mg dose be administered only in participants with excessive responses to the 200mg dose. Subsequent study visits will be scheduled no less than 2 and no more than 10 days apart. Subjects will arrive at the laboratory between 10AM and 1PM after a light breakfast and having avoided alcohol, caffeine, and nicotine for 12-hours. Subjects will remain in their wheelchair for instrumentation, which will include: 1) 3-lead electrocardiogram (ECG) for continuous recording of heart rate (HR) and respiration rate; 2) brachial BP, which will be monitored using a manual sphygmomanometer and finger arteriolar beat-to-beat BP, which will be recorded using photoplethysmography with a cuff placed around the middle or index finger of the left hand. Seated cardiovascular hemodynamic assessments will be monitored and recorded at 15-minute intervals for 4-hours, and the side effects questionnaire (Appendix 4) will be administered hourly during the 4-hour study. Individuals who do not respond to droxidopa with a normal seated SBP will be excluded from Study 2. Each study visit will take about 5 hours.

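### Study 1 gives the 100 mg step-down on the 4-hour mean SBP but judges response at 60-120 minutes, so a participant above range on 200 mg can fail to qualify for it (minor rule inconsistency)

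*Protocol*

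**What the plan says.** The Protocol's Study 1 section starts open-label dosing at 200 mg. "The dose will be adjusted upwards by 100 mg on subsequent visits until" one of four stop rules is met:

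1. mean SBP at 60-120 minutes is in range (111-139 mmHg for men, 101-139 for women);
2. seated pressure stays at or above 140/100 mmHg for at least 30 consecutive minutes;
3. 800 mg is reached without an adequate response;
4. drug-related side effects are intolerable.

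The 60-120 minute window also defines the endpoint for Hypothesis 1.1 (Protocol, Data Analysis; Combined protocol and SAP, item 17a).

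The same Study 1 paragraph defines the step-down group differently: "Participants with an excessive response to the 200mg dose, i.e., average 4-hour SBP above 139". It restricts the lower dose to that group: "we request the addition of the 100mg dose be administered only in participants with excessive responses to the 200mg dose". The combined document does not mention the 100 mg step.

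On what follows from non-response, Study 1 says: "Individuals who do not respond to droxidopa with a normal seated SBP will be excluded from Study 2".

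On the time course, the background section reports from the earlier 400 mg trial in SCI that "by 4-hours post-drug BP was not significantly different from pre-drug levels".

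**The concern.** The 100 mg dose exists for people who respond too strongly to 200 mg, but its trigger uses a different averaging period from the one that decides whether the response was too strong. A 4-hour mean includes early and late readings. If the effect has faded by the end of the visit, those readings pull the mean down, and someone clearly above range at 60-120 minutes need not reach the trigger.

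Two things can then happen under the written rules:

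- **Elevation sustained for 30 minutes.** Stop rule 2 ends titration. The person counts as not normalized in Hypothesis 1.1 and does not enter Study 2, without having tried the dose added for over-responders.
- **Elevation not sustained.** None of the four stop rules applies and the step-down does not apply, so the literal text raises the dose to 300 mg in someone already above range.

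The second outcome matters more. The Protocol itself describes this population as prone to dangerous, sometimes silent, pressure surges.

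**Working it through.** The plan gives no figure to reproduce here. The check asks how far the two windows can diverge, then how often that might matter.

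**Can the trigger be missed?** Study 1 records seated haemodynamics every 15 minutes for 4 hours. Counting time 0, that is 17 readings, of which 5 (60, 75, 90, 105 and 120 minutes) fall in the response window. If the window mean is M, the 4-hour mean exceeds 139 only if the other 12 readings average more than

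(139 × 17 − 5M) / 12.

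| Window mean M (mmHg) | Other 12 readings must average above | With 16 readings (time 0 omitted), other 11 must average above |
|---|---|---|
| 145 | (2363 − 725)/12 = 136.5 | 136.3 |
| 150 | (2363 − 750)/12 = 134.4 | 134.0 |
| 160 | (2363 − 800)/12 = 130.25 | 129.5 |

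The other readings include the pre-dose value (in the 17-reading version), the early values and all those after 120 minutes.

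As an illustration, assume a profile that starts at 105 mmHg, rises linearly to 60 minutes, stays flat to 120 minutes and returns linearly to 105 at 240 minutes. The shape is an assumption, chosen to fit the reported waning.

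| Window mean | 4-hour mean, 17 readings | 4-hour mean, 16 readings |
|---|---|---|
| 145 | 128.5 | 130.0 |
| 150 | 131.5 | 133.1 |
| 160 | 137.4 | 139.4 |
| 170 | 143.2 | 145.6 |

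On 17 readings, 145 to 160 all miss the trigger and 170 meets it. On 16 readings, 160 just meets it. Under such a profile the largest over-responders get 100 mg and the milder ones do not.

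**Can stop rule 2 also be missed?** At 15-minute spacing, 30 consecutive minutes needs three readings in a row. Window readings of 150, 150, 130, 150, 150 average 730/5 = 146. If the readings at 45 and 135 minutes are below 140, they contain no run of three. Rule 2 is also missed with SBP at 150 and diastolic below 100, if 140/100 is read as requiring both.

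**How often?** The documents do not allow a count; they give no individual 200 mg responses. What they do give points to few cases:

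- In the preliminary data, normotensive readings were 18.9% at 200 mg against 19.3% without drug. The text says of the 100 and 200 mg doses: "The proportion of SBP recordings within the normotensive range (i.e., 111-139 mmHg) did not differ from the no-drug trial".
- Even at 400 mg, "Three individuals each had a single recording of a seated SBP" of 140 mmHg or more, all in the first 30 minutes and so before the response window.
- Take 105 and 81 mmHg as the starting levels of 400 mg responders and non-responders. This is an inference, because the sentence that introduces them is broken in the text. With the stated responses of 9.0 ± 10 and 18.6 ± 16, a mean above 139 lies (139 − 105 − 9.0)/10 = 2.5 SD and (139 − 81 − 18.6)/16 = 2.5 SD above average. These are 3-hour averages in about five people per group, at twice the dose.

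One qualification is that the screening rules also admit people on an orthostatic fall, and the combined document (item 6) admits them on diastolic pressure. Such people can start above the systolic cut-offs and have less far to rise. Their number is not given.

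**Effect on Hypothesis 1.1.** One missed participant moves the proportion by at most 1/40 = 2.5 points (Protocol sample) or 1/60 = 1.7 points (combined document), and only if 100 mg would have normalized them. The 95% half-width at 60% is 1.96 × √(0.6 × 0.4/n), which is 15.2 points at n=40 and 12.4 at n=60.

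**The case against.** The strongest reply is that almost nobody will be affected. The Protocol does not expect excessive responses at 200 mg in most participants, and its earlier data support that. The benefit of 100 mg is also unshown: 11.8% of readings were normotensive at that dose. The study is an unpowered pilot, and one person is unlikely to change whether an interval includes 60%. All of this stands, and it fixes the size of the point.

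Second, five readings averaging 145 to 160 will usually contain a run of three at or above 140, so stop rule 2 will usually catch the person if systolic pressure alone counts. The escalation branch is therefore narrow. In addition, dosing is open-label, the study clinician reviews all recordings at each visit (Protocol, Safety Monitoring), and individual data are reviewed in real time (Combined protocol and SAP, item 14d). A reader might infer that participants above range will actually be escalated. The documents do not support that, and staff may well hold the dose. But these are general provisions, and none says what the next dose should be.

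Third, ending dosing after sustained hypertension is a defensible safety choice. A reader might infer that everyone stopped under rule 2 at 200 mg should be offered 100 mg. That goes too far: it would extend re-dosing regardless of the window mean. The narrower point survives, because a 4-hour mean above 139 will usually also involve sustained systolic elevation. The plan therefore already accepts a lower dose for some of these people and selects them on a window that response is not judged on.

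**Conclusion.** This is a minor but real inconsistency. The written rules can deny 100 mg to a participant who is above range on 200 mg by the study's own response criterion, and when elevation is not sustained they literally raise that person's dose. The possibility follows from the text and the reading schedule alone. Its plausibility rests on the waning reported at 400 mg, and the profile figures rest on an assumed curve.

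The number affected is unknown and probably very small. A reader might infer that the Hypothesis 1.1 estimate is materially distorted. It is not: the ceiling of 2.5 or 1.7 points per person is small beside a half-width of about 15 or 12 points. Nor is the safety endpoint biased, since a person with sustained hypertension at 200 mg is an event for Hypothesis 1.2 whether or not 100 mg follows. The reason to act is dosing safety and coherent rules.

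**What to change.** Amend the Study 1 text in three places:

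- Define an excessive response to 200 mg as a 60-120 minute mean SBP above 139 mmHg. Such participants are given 100 mg, subject to clearance by the study clinician if they also had sustained elevation.
- State that a 60-120 minute mean above 139 mmHg at any dose ends upward titration.
- State that sustained hypertension at 200 mg remains a Hypothesis 1.2 event whatever happens at 100 mg.

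With the trigger in the response window, everyone above range on 200 mg meets the definition and the gap closes. The cost is a wording amendment, possibly a few extra 100 mg visits, and a clinician decision before re-dosing after sustained elevation. No new measurements are needed, because the 15-minute readings are already taken.
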